5.11.3 Serious Adverse Events and Death

SAE will be provided by treatment group. SAE will be provided by subgroups defined in Section 5.5. As for C-SSRS, scores reported in Baseline and Prior to study page of CRF will be handled as baseline score. Scores reported in Since Last Visit and Since Study Start

page of CRF will be summarized by visit when the data is recorded. The following summary tables of SAEs will be provided:

- A summary of incidence of serious AEs (SAEs) by SOC and PT.
- A summary of incidence of SAEs leading to discontinuation by SOC and PT.
- A by-subject listing for all deaths.
- A summary of C-SSRS.
- A by-subject listing of C-SSRS.

5.11.4 AESI: ALT/AST, Infection Agent Transmission and Selected AEs

AESI are defined in the protocol as follows and collected in the eCRF using a specific question. The following summary tables and listings will be provided:

- A summary of AESI by SOC and PT.
- Suspected transmission of an infectious agent by the study drug.
- A by-subject listing of all AESI.
- A by-subject listing for infection (SOC: Infections and infestations) medicated by IV treatment.
- A by-subject listing for opportunistic infection (defined by MedDRA basket in Appendix) medicated by PO treatment.

AST and ALT will be categorized into four group (>3-5 xULN, 6-10 xULN, 11-20 xULN and 21- xULN) based on maximum post-baseline levels within baseline and post-baseline respectively for each test by maximum post-baseline levels for total bilirubin and alkaline phosphatase (total bilirubin \leq 2xULN, total bilirubin $>$ 2xULN, total bilirubin $>$ 2xULN and alkaline phosphatase $<$ 2xULN, total bilirubin $>$ 2xULN and alkaline phosphatase \leq 5xULN). The denominator is the number of subjects with any valid assessment at baseline and post-baseline respectively. Subjects with AST or ALT results fulfilling criteria for more than one category are counted only once, in the category indicating the highest elevation level within baseline and post-baseline.

- Summary of AST and ALT Results.

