#### 5.1.1.4 Liver Enzyme and Bilirubin Elevations and Potential Risk of Hepatotoxicity

Reversible elevations of AST and total bilirubin were each observed in 2 healthy subjects and reversible elevation of ALT in 1 healthy subject out of 72 healthy subjects in the Phase 1 single ascending dose study (SA-001JP).

*In the Phase 3 studies, mild and moderate elevations of liver transaminases have been observed with satralizumab treatment. Most elevations were  $<5 \times$  ULN and resolved while on treatment with satralizumab. Elevations of ALT or AST  $>3 \times$  ULN were not associated with increases in total bilirubin.*

It has been reported that IL-6 appears to have a hepatoprotective effect on various forms of liver injury and promotes hepatocyte regeneration. Patients with elevated transaminases ALT or AST  $>1.5x$  ULN will be excluded from this study.

Liver function markers should be closely monitored when satralizumab is administered, especially concomitantly with hepatotoxic drugs or administered in patients with elevated transaminases.

Recommended dose interruptions based on transaminases are shown in [Table 4](#).

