#### **5.3.5.6 Abnormal Liver Function Tests**

The finding of an elevated ALT or AST (>3x ULN) in combination with either an elevated total bilirubin (>2x ULN) or clinical jaundice in the absence of cholestasis or other causes of hyperbilirubinemia is considered to be an indicator of severe liver injury. Therefore, Investigators must report as an AE the occurrence of either of the following:

- ALT or AST >3 × ULN in combination with total bilirubin >2 × ULN
- ALT or AST >3 × ULN in combination with clinical jaundice

Any other reason than study drug-induced liver injury should be checked, such as viral hepatitis A, B, or C, preexisting or acute liver disease, or another drug capable of causing the observed injury in case these have any clinical probability. The most appropriate diagnosis or (if a diagnosis cannot be established) the abnormal laboratory values should be recorded on the Adverse Event page of the eCRF (see Section 5.3.5.1) either as an SAE or a non-serious AESI (see Section 5.4.2) and must be reported to the Sponsor within 24 hours after learning of the event,

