5.6 Demographic and Other Baseline Characteristics

Summary tables and listing will be provided as follows for ITT, PK-PPS and SAF:

- Demographics will be summarized as collected at screening or baseline visit before administration of first dose of study drug and will include gender, race (American Indian/Alaska Native, Asian [Japanese], Asian [Non-Japanese], Black/African American, Native Hawaiian/other Pacific Islander, White and Other), Geographic region (Asia, Europe/other), age (years), age category (<18, ≥18), ethnicity, racial subgroup, height, body weight (the first and the third quartiles of body weight will be presented), body mass index (BMI, kg/m²), BMI category (<18.5, ≥18.5 to <25, ≥25 to <30, and ≥30 kg/m²), Baseline ARR (1, >1) , AQP4 status at screening (positive, negative), Diagnosis (NMO, NMOSD) and Baseline treatment (azathioprine, mycophenolate mofetil, oral corticosteroids, azathioprine + oral corticosteroids, mycophenolate mofetil + oral corticosteroids) by treatment group and overall.

- A by-subject listing of demographic data.

Age will be calculated as the number of complete years between a subject's birth date and the date of the first informed consent.

The subgroup summary tables will be presented for ITT and SAF by the defined variables with the exception of ADA status (See section 5.5).

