5.11.9 Clinical Laboratory Evaluation

For continuous laboratory measurements including hematology, clinical chemistry, and urinalysis, summary using descriptive statistics of the actual values and their change from baseline will be presented by treatment group at each visit. The laboratory tests to be performed are presented in Table 4-4.

When analyzing categorical data, the number and percentage of subjects in each category will be presented. In addition, shift tables may be used to evaluate the number and percentage of subjects having a different post-baseline status when compared to their baseline status.

A subject data listing will be provided for all laboratory data. Values outside the normal range will be flagged within the listing. A subject data listing will also be provided for all treatment emergent marked laboratory abnormalities (see Section 7.1).

The following summaries, listings and figures will be provided:

- A summary of each laboratory parameter in Table 4-4 and change from baseline will be provided by visit.
- A shift table based on the normal range for each laboratory parameter will be presented by double-blind period endpoint value relative to baseline by treatment group.
- A by-subject listing of laboratory parameters.

The summaries above will be provided by treatment group.

Table 4-4 Laboratory measurements

Hematology	Clinical chemistry	Urinalysis	Complement
Hematocrit	Calcium	Glucose	Complement tests (C3, C4 and CH50)
Hemoglobin	Phosphorus	Protein	
International normalized ratio	Serum electrolytes (sodium, potassium, chloride)	Urinary occult blood	
Platelet count	Ferritin	Urobilinogen	
Red blood cell (RBC) count	Albumin		
WBC count	Total serum protein		
Absolute differential count (neutrophils, eosinophils, lymphocytes, monocytes, basophils, other cells)	Blood urea nitrogen (BUN)		
	Creatinine		
	Uric acid		
	Alkaline phosphatase		
	AST		
	ALT		
	GGT		
	Total bilirubin		
	Fibrinogen		

	Lactate dehydrogenase (LDH) Total cholesterol Low density lipoprotein (LDL) cholesterol High density lipoprotein (HDL) cholesterol Triglycerides Creatine kinase (CK)		
--	--	--	--

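### SAP 5.11.4: the ALT/AST bands leave gaps at 5–6, 10–11 and 20–21 x ULN, so a subject whose maximum falls there enters no row but stays in the denominator

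*SAP*

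**What the plan says.** SAP 5.11.4 plans a summary of AST and ALT by elevation category, crossed with categories of total bilirubin and alkaline phosphatase. The categories apply to each subject's maximum: "AST and ALT will be categorized into four group (>3-5 xULN, 6-10 xULN, 11-20 xULN and 21- xULN".

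Two further rules in the section matter here. On the denominator: "The denominator is the number of subjects with any valid assessment at baseline and post-baseline respectively". On multiple results: "Subjects with AST or ALT results fulfilling criteria for more than one category are counted only once, in the category indicating the highest elevation level".

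Elsewhere the SAP bands continuous measures without holes. Section 5.6 has "BMI category (<18.5, ≥18.5 to <25, ≥25 to <30, and ≥30", and the QTc categories in 5.11.10 adjoin in the same way. Protocol Table 4 (hepatic enzymes) also uses adjoining ranges, passing from >3 to 5 x ULN directly to >5 x ULN.

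**The concern.** The end points 5 and 6, 10 and 11, and 20 and 21 suit a variable that takes whole numbers only. A laboratory value divided by its upper limit does not. If the table is programmed to the text, a subject with a maximum in a gap disappears from the numerator but not from the denominator.

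All three gaps lie above 5 x ULN, so the error runs in one direction. The number of subjects above 5 x ULN, which is the boundary of the top row of Protocol Table 4, could not be read reliably from the table.

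This matters most for a transaminase rise without raised bilirubin or jaundice. Protocol 5.1.1.4 says that "mild and moderate elevations of liver transaminases have been observed with satralizumab treatment", and that elevations above 3 x ULN did not go with a rise in total bilirubin. A rise of that kind does not meet the combined liver criterion for an AESI in Protocol 5.2.3 and 5.3.5.6. For it, the table in 5.11.4 is the only SAP table graded by multiple of ULN. The shift table in 5.11.9 works differently: "A shift table based on the normal range for each laboratory parameter will be presented by double-blind period endpoint value".

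**Working it through.** The plan states no figure to reproduce, so the check applies the bands as written to test values.

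**Inputs**
- Bands, SAP 5.11.4: (3, 5], [6, 10], [11, 20] and [21, ∞) x ULN.
- Value classified: the subject's maximum divided by ULN. No rounding rule is stated.
- Reference upper limits, SAP 7.1: ALT 55 (men) and 30 (women) U/L; AST 40 (men) and 25 (women) U/L. Section 5.11.4 does not say which ULN it uses, so the U/L figures below are an illustration. The gaps in multiples of ULN do not depend on them.
- Arm size: about 70 patients randomized 1:1, so 70/2 = 35.

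**Step 1: which multiples find a row**

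| Maximum (x ULN) | Band as written | Contiguous band |
|---|---|---|
| 3.01; 5 | >3-5 | >3 to ≤5 |
| 5.01; 5.5; 5.99 | none | >5 to ≤10 |
| 6; 10 | 6-10 | >5 to ≤10 |
| 10.5 | none | >10 to ≤20 |
| 11; 20 | 11-20 | >10 to ≤20 |
| 20.5 | none | >20 |
| 21 | 21- | >20 |

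The uncovered values above 3 x ULN are exactly the open intervals (5, 6), (10, 11) and (20, 21). Contiguous bands leave nothing above 3 x ULN unassigned.

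**Step 2: the gaps in U/L** (k × ULN to (k+1) × ULN, ends excluded)

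| Test | ULN | k = 5 | k = 10 | k = 20 |
|---|---|---|---|---|
| ALT, men | 55 | 275–330 | 550–605 | 1100–1155 |
| ALT, women | 30 | 150–180 | 300–330 | 600–630 |
| AST, men | 40 | 200–240 | 400–440 | 800–840 |
| AST, women | 25 | 125–150 | 250–275 | 500–525 |

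Examples: 300/55 = 5.45 and 220/40 = 5.50.

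The SAP 7.1 transformation of female values to the male range does not close the gaps. With lower limits of zero it is a pure rescaling, R_T = (R_U / I_H) × S_H, so the multiple of ULN is unchanged. For a female ALT of 165 U/L, 165/30 = 5.5. The transformed value is 5.5 × 55 = 302.5 U/L, and 302.5/55 = 5.5.

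**Step 3: do the other rules in 5.11.4 repair it?** The highest-category rule applies to subjects who meet more than one category, so it gives no row to a maximum that meets none. The denominator rule keeps every subject with a valid assessment.

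**Step 4: would rounding repair it?**
- Nearest integer: 5.45 becomes 5 and goes to the first band. But 3.2 becomes 3 and leaves the >3 band, contrary to the SAP's own lower bound.
- Rounding up: 5.45 becomes 6 and goes to the second band, which gives the same result as contiguous bands.

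The SAP states neither. A maximum of 5.45 x ULN can therefore fall in no row, the first row or the second row, depending on the programmer.

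**Step 5: size.** One subject in an arm of 35 is 1/35 = 2.86 percentage points.

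**The case against.** The strongest reply is that this is loose notation. The second band was almost certainly meant as >5 to 10, and so on. The SAP's introduction says it is to be read together with the protocol, and Protocol Table 4 adjoins at 5 x ULN. A sensible programmer would close the gaps without being told. A literal programmer might also put a subject with a 5.5 maximum and another result of 4.0 into the >3-5 band, so absence is not the only outcome.

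Other outputs would also show such a subject:
- SAP 5.11.9 plans listings of all laboratory data and of marked abnormalities, and by-visit summaries, which include the maximum.
- Protocol 6.6 plans counts of patients with marked abnormalities. The limits in SAP 7.1 (ALT 110, AST 80 U/L) are twice the male ULN, so every gap value exceeds them, although a rise of at least 50% from baseline is also required.
- A laboratory result that changes study drug is reported as an AE, and SAP 5.11.2 tabulates AEs leading to interruption or discontinuation.
- A combined transaminase and bilirubin case is reported "either as an SAE or a non-serious AESI".

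The table is descriptive, with no test or decision rule attached.

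Most of this stands, and it limits the consequence: the information is not lost to the study. It does not make the stated rule correct. The likely intent is an inference, and Table 4 supports it only at the first gap. Placing a 5.5 maximum in >3-5 would also understate it. None of the other outputs counts subjects by multiple of ULN.

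**Conclusion.** The concern holds. Followed exactly, SAP 5.11.4 drops subjects with maxima in (5, 6), (10, 11) or (20, 21) x ULN from the table while keeping them in the denominator. Any resulting error understates the larger elevations.

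The size is 2.9 percentage points per affected subject in an arm of about 35, and less in the pooled All SA237 table, where the denominator is larger. The documents give no distribution of maxima, so no expected number is claimed. Protocol 5.1.1.4 says that most elevations were below 5 x ULN, which suggests that few subjects, possibly none, are affected.

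The conclusion rests on reading the bands as printed, with no rounding convention supplied elsewhere. The error is confined to this table and its cross-tabulation. It should be corrected, but it does not threaten the trial's main conclusions.

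**What to change.** In SAP 5.11.4, replace the four bands with >3 to ≤5, >5 to ≤10, >10 to ≤20 and >20 x ULN. State that they apply to the unrounded ratio of each subject's maximum to ULN, and keep the highest-category rule. It would also help to name the ULN used, since the section does not.

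The cost is one line in the SAP and the matching format statement in the table program. The change matches the 5 x ULN cut point in Protocol Table 4 and alters no clinical rule.

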5.11.5 Infections, Serious Infection, Opportunistic Infection

- Serious adverse event in “SOC: Infections and infestations” will be summarized. Opportunistic infections are defined by MedDRA basket in Appendix.. Serious infection will be provided per 100 subject-year by treatment group during the double blind period. The patient-years will be based on the double blind period for safety analysis (see section 5.2). The rate per 100 subject-years by treatment group (along with the 95% CI) will be calculated for serious infections.

The number of serious infections per 100 subject-years is calculated as:

Total number of serious infections / Total number of subject-years \times 100

The 95% CI for the number of serious infections per 100 subject-years is calculated as follows:

Exact lower 95% confidence limit = $\text{chisq}(p = 0.025, df = 2Y) / (2T)$

Exact upper 95% confidence limit = $\text{chisq}[p = 0.975, df = 2(Y + 1)] / (2T)$

where Y is the total number of serious infections, T is total number of subject-years at risk and $\text{chisq}(p, df)$ is the quantile of the upper tail probability of the X² distribution on df degrees of freedom. This approach has the advantage of providing an estimate for the upper 95% confidence limit even when the total number of serious infections is zero.

The following summary tables will be provided.

- A summary of serious infection by SOC and PT.
- Rates of serious infections by 100 patient-years.
- A by-subject listing of Infections.
- A by-subject listing of Opportunistic Infections.

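### The confidence interval specified for the serious-infection rate takes its chi-square quantiles from the wrong tail and leaves out the factor of 100

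*SAP*

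**What the plan says.** SAP Section 5.11.5 sets the serious-infection rate in each treatment group as "Total number of serious infections / Total number of subject-years", multiplied by 100. It introduces the interval with "The 95% CI for the number of serious infections per 100 subject-years is calculated as follows". The two limits are then:

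- lower: chisq("p = 0.025, df = 2Y) / (2T")
- upper: chisq["p = 0.975, df = 2(Y + 1)] / (2T")

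The definition of chisq settles which tail p refers to: the function "is the quantile of the upper tail probability of the" chi-square distribution. Y is the event count and T the exposure in subject-years, not in hundreds of subject-years. Neither limit carries a factor of 100. The section recommends the method for "providing an estimate for the upper 95% confidence limit even when the total number of serious infections is zero".

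Nothing else in the SAP restates or corrects the formula. The SAS code in Appendix 7.7 covers the log-rank test, Cox model, MMRM and ANCOVA only.

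**The concern.** There are two separate defects.

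1. **Tail.** The exact Poisson limits use the 0.025 cumulative quantile on 2Y degrees of freedom and the 0.975 cumulative quantile on 2(Y + 1). The SAP has these p values and degrees of freedom, but its definition of chisq measures p from the upper tail. The large quantile then goes to the lower limit and the small one to the upper.
2. **Scale.** Dividing by 2T, with T in subject-years, gives limits per 1 subject-year. The estimate and the stated target are per 100.

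Serious infection heads the list of risks in Protocol Section 5.1.1, and Protocol Section 5.1.1.1 warns that satralizumab may mask signs of infection. With one or more events, a literal calculation gives a visibly reversed interval. With no events it gives an upper limit close to zero, which looks plausible and overstates safety. That is the very case for which the SAP recommends the method.

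**Working it through.** **Inputs.** The formulas are those of SAP Section 5.11.5. The SAP gives no worked interval, so there is no figure to reproduce. Y (events) and T (subject-years) are assumptions: Y = 0 or 3, with T = 60 as the main case and 50, 70 and 100 as the range.

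**Why T near 60 is reasonable.** The sample-size assumptions (SAP Section 5.14, Protocol Section 6.2) are 35 patients per arm, a placebo hazard of 0.4184 per year, a hazard ratio of 0.335, 10% dropout over 2 years, one year of accrual and a further 1.5 years of follow-up.

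- Satralizumab relapse hazard: 0.4184 × 0.335 = 0.1402.
- Dropout hazard: −ln(0.9)/2 = 0.0527.
- Sum: r = 0.1928.
- With uniform accrual, maximum follow-up t runs from 1.5 to 2.5 years. Averaging (1 − exp(−r t))/r over that range and multiplying by 35 gives about 57.9 subject-years.

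**Quantiles needed**

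| | Cumulative (correct) | Upper tail (as defined) |
|---|---|---|
| Y = 3, p = 0.025, df = 6 | 1.237 | 14.449 |
| Y = 3, p = 0.975, df = 8 | 17.535 | 2.180 |
| Y = 0, p = 0.975, df = 2 | 7.378 | 0.0506 |

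**Y = 3, T = 60; rate = 3/60 × 100 = 5.0 per 100**

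- As written: lower = 14.449/120 = 0.120; upper = 2.180/120 = 0.018.
- Correct: lower = 100 × 1.237/120 = 1.03; upper = 100 × 17.535/120 = 14.61.

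**Y = 0, T = 60**

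- As written: upper = 0.0506/120 = 0.00042, or 0.042 per 100 after rescaling.
- Correct: upper = 100 × 7.378/120 = 6.15 per 100.
- Ratio on a common scale: 7.378/0.0506 ≈ 146, whatever T is.

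**Other values of T**

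| T | Y | Rate per 100 | As written: lower, upper | Correct, per 100 |
|---|---|---|---|---|
| 50 | 3 | 6.0 | 0.144, 0.022 | 1.24 to 17.53 |
| 70 | 3 | 4.29 | 0.103, 0.016 | 0.88 to 12.52 |
| 100 | 3 | 3.0 | 0.072, 0.011 | 0.62 to 8.77 |
| 70 | 0 | 0 | 0, 0.00036 | 0 to 5.27 |

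The lower limit at Y = 0 is taken as 0 by convention. T cancels when the two limits are compared, so the reversal depends on Y alone; it occurred for every Y tested from 1 to 5000. The corrected limits were checked against exact Poisson probabilities, and each leaves 0.025 in its tail (at Y = 0, the upper limit only).

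**Partial repairs fail**

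- Factor of 100 only (Y = 3, T = 70): the limits stay reversed, at 10.32 and 1.56.
- Tail only (Y = 3, T = 70): 0.0088 to 0.1252, beside a rate of 4.29 per 100.
- Factor of 100, with the two limits swapped (Y = 3, T = 60): 1.82 to 12.04 instead of 1.03 to 14.61. This is too narrow, because each limit now has the other's degrees of freedom. Taking the interval at Y = 0 as 0 to the written upper limit, actual coverage is about 55%, 81% and 92% when 1, 2 and 3 events are expected, against a nominal 95%.

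**The case against.** The intended method is easy to recognise. The limits are labelled exact, and the p values and degrees of freedom are those of the standard Poisson interval; only the explanation of chisq is wrong. A programmer calling a default cumulative quantile function would avoid the tail error without noticing it. The unit of 100 subject-years is stated repeatedly, and SAP Section 5.1 requires independent checking of tables, which should catch a reversed interval. The interval enters neither the primary test nor the testing sequence in SAP Section 5.10.1.4. Serious infections are also tabulated and infections are listed by subject, and SAP Section 5.11 allows listings alone if events are few.

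Much of this stands, and three limits on the claim follow from it:

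- The reversal needs at least one event. With none, only the upper limit is wrong.
- The written limits fail to contain the estimate because of their order and unit. On a common scale the estimate does lie between the two numbers (0.050 between 0.018 and 0.120 in the T = 60 example).
- The 146-fold error requires zero events and literal upper-tail coding.

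The defects themselves are not removed. A programmer who quietly uses cumulative quantiles departs from the SAP, and a second programmer following the text would get a different answer. The default function does nothing about the missing 100. The zero-event result is also the one that checking is least likely to catch.

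**Conclusion.** The concern holds. The formula in SAP Section 5.11.5 cannot give a valid 95% interval per 100 subject-years as defined: the limits are reversed for any positive count and are on the wrong scale. At zero events the upper limit is about 146 times too small even after rescaling. The direction of both errors does not depend on the assumed Y and T; only the illustrative limits do.

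The consequence is confined to one descriptive safety interval. The point estimate is specified correctly and the efficacy conclusions are unaffected. It should still be corrected, because it is a plain error in the only adverse-event rate that the SAP reports with a confidence interval.

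**What to change.** In SAP Section 5.11.5:

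- define chisq(p, df) as the quantile with cumulative (lower-tail) probability p;
- write the limits as 100 × chisq(0.025, 2Y)/(2T) and 100 × chisq(0.975, 2(Y + 1))/(2T);
- state that the lower limit is 0 when Y = 0.

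The cost is a change to the SAP wording and one line of code. If the tables have already been produced, confirm which tail and which scale were programmed, and rerun them if either differs from the corrected text.
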